8.2. Exploratory Efficacy Analyses

8.2.1. Responder Across Endpoints

For appraisal of trends across secondary efficacy endpoints, a nine-panel plot for each participant with a single panel for each of the following efficacy endpoints will be produced:

- Mayo Endoscopy Remission
- UCEIS Total Score,
- FCP,
- CRP,
- Modified Riley Scale Total Score
- Geboes Index Total Score,
- Total Mayo Score,
- Partial Mayo Score
- 3-domain Mayo Score.

8.2.2. Probabilities of Success

Probabilities of success may be determined, based on the data observed in the study, where the definition of success will be dependent on the endpoint. For example, what is the probability that we would observe a certain proportion of Mayo Endoscopic Remission (0 or 1) (i.e., comparatory rate), based on the data that we have observed in this study.

A Bayesian approach will be employed to determine a 95% credible confidence interval around the observed probability of success with a flat Beta (1, 1) prior. Any such analyses will be done by GSK II Clinical Statistics after unblinding of the interim data and thus will be deemed post-hoc.

8.3. Exploratory Pharmacodynamic / Efficacy Analyses

If deemed appropriate, the relationship between the biopsy biomarkers and efficacy endpoints will be explored further using multivariate statistical methods and/or Bayesian methodology as recommended by the GSK PCPS Experimental Medicine working group. The consistency in the changes over time between the endpoints will also be assessed. Any such analyses will be defined after unblinding of the interim data and thus will be deemed post-hoc.

9. PHARMACOKINETIC ANALYSES

9.1. Pharmacokinetic Analyses

9.1.1. Endpoint / Variables

9.1.1.1. Drug Concentration Measures

PK plasma and biopsy tissue Concentration data for GSK2982772 will be summarised and listed, no statistical analysis will be conducted. Summary statistics of GSK2982772 concentration by Day (1, 43, and 85) and nominal blood sampling time will be determined. PK blood samples are taken pre-dose on Day 43 and post-dose on Days 1 and Day 43 at the following time points: 1, 2, 4, and 6 hours and trough on Day 85 or Early Withdrawal.

PK data will be summarised for Parts A and B by randomised treatment.

Refer to [Appendix 5: Data Display Standards & Handling Conventions \(Section 12.5.3 Reporting Standards for Pharmacokinetic\)](#).

Table 7 Overview of Planned Pharmacokinetic Analyses

Endpoints	Untransformed				Log-transformed			
	Summary		Individual		Summary		Individual	
	T	F	F	L	T	F	F	L
Pharmacokinetic								
Plasma Drug concentration	Y	Y ^[1] 2	Y ^[1]	Y				
Biopsy Tissue Drug concentration	Y	Y ^[1] 2	Y ^[1]	Y				

NOTES:

- T = Table, F = Figure, L = Listings, Y = Display generated.
 - Summary = represents TF related to any summaries (i.e. descriptive statistics) of the observed raw data.
 - Individual = represents FL related to any displays of individual participant observed raw data.
- 1: Linear and Semi-Log plots will be created on the same display.
2: Separate Mean (\pm SE) and Median plots will be generated.

Since the half-life of GSK2982772 is short (2-3h), the duration of time between the Day 43 clinic visit and the usual dosing time may result in the reported “pre-dose” concentration being lower than the true “pre-dose” or trough concentration (e.g. if the usual dose time was 7am and the clinic visit was 10am the “pre-dose” sample collected at 10 am would be approximately $\frac{1}{2}$ that of the true “trough” concentration assuming a 3 hour half-life). Therefore, the predicted “trough” concentration will be calculated using the following equation-

$$C_{trough} = C_{predose} + (e^{-(k_e \times t)})$$

where

- C_{trough} = predicted trough concentration prior to usual dosing time
- $C_{predose}$ = observed “pre-dose” concentration collected at the clinic
- t = time in hours between pre-dose blood sample collection and time of dosing (assumed to be 7am)
- k_e = elimination rate constant ($0.693 / t_{1/2}$), ($t_{1/2}$ assumed to be 2.5h)

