No endpoint and derivations for the Roberts Histology Index (RHI) was explicitly mentioned in the protocol. The protocol endpoints section states: Change from baseline on histologic severity including but not limited to MRS and Geboes. Roberts will also provide GSK with the RHI alongside the MRS and Geboes.	Relevant definitions for the RHI and required summaries were added to the RAP	To enable analysis of the RHI data.
GSK2982772 plasma concentrations will be summarised descriptively by day and nominal sampling time (Pre-dose on Day 43 and at 1, 2, 4, and 6 hours post dose on Days 1 and 43 and trough on Day 85 or Early Withdrawal).	The predicted trough concentration at 7am on Day 43 will be calculated using the observed pre-dose concentration at the time of the PK sample (see Section 9.1.1.1 for calculations) The predicted Day 43 trough concentration will be used in PK/PD assessments instead of the observed Day 43 Pre-Dose concentration	Since the half-life of GSK2982772 is short (2-3h), the duration of time between the Day 43 clinic visit and the usual dosing time (assumed to be 7am for all subjects) may result in the reported "pre-dose" concentration being lower than the true "trough concentration"

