9.3. Pharmacokinetic/Pharmacodynamic Analyses

The relationship between GSK2982772 predicted trough concentration and the following variables will be explored graphically:

- Target engagement from the corresponding blood/biopsy tissue sample;
- Change from baseline in continuous efficacy endpoints (Total Mayo Score, Partial Mayo Score, 3-domain Mayo Score, UCEIS Total Score, Modified Riley Scale Score, Geboes Index Total Score, RHI Score, CRP and FCP).

Box plot of GSK2982772 concentrations in participants not achieving a Mayo Endoscopy Remission and participants achieving a Mayo Endoscopy Remission.

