12.10.9. Pharmacokinetic Tables

Pharmacokinetic: Tables					
No.	Population	IDSL / Example Shell	Title	Programming Notes	Deliverable [Priority]
PK concentration data					
4.1.	PK	PK01	Summary of GSK2982772 Concentration-Time Data (ng/mL)	Separate summaries for blood and biopsy tissue samples. Pre-dose: Day 43, Post-dose: Day 1 and 43 at 1, 2, 4 and 6 hours.	IA SAC [1] SAC [1]
			Summary of GSK2982772 Predicted Trough Concentrations (ng/mL)	Predicted trough Day 43	

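### As the text reads, the predicted-trough equation in SAP Section 9.1.1.1 adds e^−(ke × t) to the pre-dose concentration, which does not reproduce the SAP's own half-life example; confirm the operator and state the sign of t (minor, low confidence)

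*SAP*

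**What the plan says.** Section 9.1.1.1 explains that the drug's half-life is short (2 to 3 h), so a clinic sample drawn after the usual dosing time may give a "concentration being lower than the true" trough. It illustrates this: "if the usual dose time was 7am and the clinic visit was 10am the" sample would be about half the true trough under a 3 h half-life.

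The equation follows. It opens "C_{trough} = C_{predose" and continues, after a plus sign, with e^−(ke × t) in its own brackets. Here ke is 0.693 divided by the half-life, the half-life is "assumed to be 2.5h", and t is the number of hours between the sample and the dosing time, taken as 7am. The sign of t is not stated.

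The derived value is used elsewhere in the SAP:

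- Section 2.1, Table 1: "The predicted Day 43 trough concentration will be used in PK/PD assessments instead of the observed Day 43 Pre-Dose concentration". This entry sends the reader to Section 9.1.1.1 for the calculation, and the equation is not repeated anywhere else.
- Section 9.3: "The relationship between GSK2982772 predicted trough concentration and the following variables will be explored graphically".
- Section 12.10.9, under Table 4.1: "Summary of GSK2982772 Predicted Trough Concentrations (ng/mL"), which also fixes the unit.

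**The concern.** The equation and the example stand in the same subsection and disagree. The example calls for a multiplicative correction that grows with the delay. The equation as it reads adds a pure number between 0 and 1 to a concentration in ng/mL, and that number shrinks as the delay grows.

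A programmer who followed the equation literally would leave almost all of the shortfall in place, unless concentrations were around 1 ng/mL or lower. The delay is part of the design: participants skip the home morning dose on Day 43 and are dosed at the site after the pre-dose assessments. Delays will presumably differ between participants. An uncorrected value would then carry visit time into the exposure axis of the PK/PD plots, which is what the derivation is meant to prevent.

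**Working it through.** **Inputs, all from SAP Section 9.1.1.1 unless noted**

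- Example: dose time 7am, sample 10am, so t = 3 h; half-life 3 h; sample about half the trough, so C_trough / C_predose ≈ 2.
- Equation: ke = 0.693 / half-life, with half-life 2.5 h; stated range 2 to 3 h.
- Unit: ng/mL (Section 12.10.9).
- Concentration level: not given in the SAP. The 100 ng/mL used below is an assumption, and a range is shown.

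**Step 1. Try to reproduce the SAP's example.**
ke = 0.693 / 3 = 0.231 per h, so e^−(0.231 × 3) = 0.500. With an assumed C_predose of 100 the example requires about 200.

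- Sum, as it reads: 100 + 0.500 = 100.5. Not reproduced.
- Division: 100 / 0.500 = 200. Reproduced.

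The sum meets the example only by coincidence, at C_predose = 0.5.

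**Step 2. Zero delay.**
At t = 0, e^0 = 1 and no correction is needed. The sum gives 101; division gives 100.

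**Step 3. The SAP's working half-life of 2.5 h.**
ke = 0.693 / 2.5 = 0.2772 per h. For an assumed 100 ng/mL:

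| Delay (h) | e^−(ke × t) | Sum | Division |
|---|---|---|---|
| 0 | 1.000 | 101.0 | 100.0 |
| 1 | 0.758 | 100.8 | 131.9 |
| 3 | 0.435 | 100.4 | 229.7 |

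The required factor at 3 h is 1 / 0.4354 = 2.30. Over half-lives of 2 to 3 h it runs from 2.83 to 2.00. The sum at 3 h is 56% short (1 − 100.44 / 229.70).

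**Step 4. Dependence on the assumed concentration (3 h delay, 2.5 h half-life).**

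| C_predose (ng/mL) | Sum | Division | Shortfall of sum |
|---|---|---|---|
| 1 | 1.435 | 2.297 | 38% |
| 10 | 10.44 | 22.97 | 55% |
| 100 | 100.44 | 229.70 | 56% |
| 1000 | 1000.44 | 2297.0 | 56% |

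The two forms agree where C + 0.435 = 2.297 × C, that is at C = 0.435 / 1.297 = 0.34 ng/mL. Below that level the sum over-corrects.

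**Step 5. Does another detail explain the gap?**
The example uses a 3 h half-life and the equation 2.5 h. That moves the required factor only from 2.00 to 2.30, while the sum adds no more than 1 unit either way. Taking t as negative (7am minus 10am = −3 h) does not rescue the sum either: in the example it gives 100 + 2.0 = 102, not 200.

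**The case against.** The strongest objection is that the SAP may contain no plus sign at all. A plus and a division sign are easily confused when a PDF is machine-read. Mathematical text in the efficacy derivations of Appendix 6 is visibly garbled. The exponential has its own outer brackets, which are redundant after a plus but natural after a division sign, and the surrounding prose describes the division form. This stands as a real possibility. The available text cannot settle it, and for this reason confidence is low. It does not dispose of the point, because no other place in the SAP gives the division form.

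A second objection is that division is not the only form that works. If t were signed from sample to dose time, and so negative, multiplying by e^−(ke × t) would give the same factor of 2 in the example and 1 at zero delay. This is correct. Division is the answer only for t as a positive elapsed time, which is the natural reading of the definition but is not stated. The correction should therefore fix the sign as well.

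Third, the consequence is small. On concentration data the SAP says "no statistical analysis will be conducted", and the PK/PD relationships are explored only by plots. This also stands, and it limits the point to minor.

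**Conclusion.** The point is minor and held with low confidence. As the text reads, the equation does not reproduce the SAP's own example. It is also inconsistent in units, corrects when no correction is needed, and corrects less as the delay grows. At a 3 h delay with the 2.5 h half-life and an assumed 100 ng/mL, it would leave the predicted trough 56% below the value that the SAP's reasoning requires. That figure depends on the assumed concentration, as shown in the working, and on first-order elimination with t positive.

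A reader might infer that the plan's equation is proven wrong, or that the trial's efficacy or safety conclusions are at risk. The documents support neither inference. The operator may be a reading artefact. The affected outputs are limited to the predicted-trough summary under Table 4.1, the predicted-trough pages of Figures 4.8 to 4.17, and Table 6.4. Observed pre-dose concentrations are still reported, and no treatment comparison uses the predicted trough.

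**What to change.** First look at the operator in the source SAP and in the derivation program. If both divide, close the point.

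If either does not, state C_trough = C_predose / e^−(ke × t) = C_predose × e^(ke × t), and define t as positive hours from 7am to the pre-dose sample. Test the program against three values: a factor of 2.0 at 3 h with a 3 h half-life, 1.0 at t = 0, and 2.30 at 3 h with the 2.5 h half-life.

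The cost is one look at the source and one program check. If a correction is needed, it is one operator, one clarifying line on t, and a rerun of the descriptive outputs named above. No new data are required.

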8. Sigmoidoscopy may be performed on a separate day within the Day 43 visit window allowance (± 3 days). A separate visit to perform sigmoidoscopy is only allowed to accommodate scheduling. This separate visit should be done before the full Day 43 visit where PK, clinical laboratory tests and all other required Day 43 procedures are performed. Participants must not take their study medication at home in the morning before the sigmoidoscopy procedure and also the morning before the full Day 43 visit, if being done on a separate day. Dispensing of study medication must be done at the 2nd visit (if separate visits are performed).
9. Biopsy only required at Early Withdrawal visit if after at least 14 days of treatment and prior to Day 43 or if after Day 57 and prior to Day 85.
10. Participants must take study medication three times a day approximately 8 hours apart. Exact time of dosing to be recorded in diary cards. On Day 43 and 85, participants must not take their study medication at home in the morning. Participant will complete specified pre-dose assessments and then will be administered their morning dose of medication at site on Day 43. On Day 85, participants are no longer receiving study medication.
11. In Part A, participants will be randomised 2:1 to GSK2982772 60 mg or placebo three times daily for 42 days. At the Day 43 visit, all participants who have completed Part A, will move in to Part B open label treatment with GSK2982772 60 mg three times daily for 42 days.
12. If urine pregnancy test is positive, a confirmatory serum pregnancy test must be performed.
13. Urinalysis not required on Days 29, 57 and 71.
14. Participants can provide a faecal sample at any time during the screening window and up to 48 hours prior to any visit where FCP is being collected. Please see laboratory manual for full details on sample handling and procedure.
15. Blood samples for exploratory biomarkers and Target engagement. See laboratory manual for full details on sample collection, handling and shipment.
16. PK blood samples for GSK2982772 will be taken pre-dose on Day 43. Post-dose serial PK samples will be taken on Days 1 and Day 43 at the following time points: 1, 2, 4, and 6 hours and trough on Day 85 or Early Withdrawal.

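### The predicted Day 43 trough uses one assumed 7am dosing time for everyone, although dosing times are recorded: under the intended decay, +32% per hour later than 7am and −24% per hour earlier

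*SAP*

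**What the plan says.** Table 1 (SAP 2.1) and 9.1.1.1 explain that, because the half-life is short, a pre-dose sample drawn at a Day 43 clinic visit later than the usual dose may lie below the true trough. A predicted trough is therefore calculated, and Table 1 has it replace the observed Day 43 pre-dose value in PK/PD assessments.

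The delay t in that calculation is "time in hours between pre-dose blood sample collection and time of dosing (assumed to be 7am"). Table 1 makes the scope explicit: the usual dosing time is "assumed to be 7am for all subjects". The half-life behind ke is "assumed to be 2.5h", within a stated range of 2 to 3 h.

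Footnote 10 of the schedule (12.2.1) fixes spacing, not clock time: "Participants must take study medication three times a day approximately 8 hours apart". It continues: "Exact time of dosing to be recorded in diary cards". Section 2.3 likewise has participants record study medication daily on the diary card.

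The predicted trough is used in the predicted-trough summary (Table 4.1), in predicted target engagement (Table 6.4) and in Figures 4.8 to 4.17 against the efficacy endpoints. No display that varies the 7am assumption is listed.

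**The concern.** The correction exists because the gap between a participant's usual dose and the clinic sample matters at this half-life. The plan then replaces one end of that gap with a constant, although the trial has participants write down the real value. Someone who usually doses at 9am and is sampled at 10am is one hour late but is corrected as three hours late. Someone who usually doses at 6am is under-corrected.

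At stake is the plotted exposure value for each active-arm participant. With about 36 × 2/3 = 24 such participants, the scatter and box plots have little room for a multiplicative error that reflects daily routine and not exposure.

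**Working it through.** **Inputs.** Usual dosing time 7am for all, half-life 2.5 h and ke = 0.693/half-life (9.1.1.1, Table 1); stated half-life range 2 to 3 h (9.1.1.1); 36 participants randomised 2:1 (2.3). No concentrations are given in the SAP.

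**1. The plan's own example.** Usual dose 7am, sample 10am, half-life 3 h: exp(−(0.693/3) × 3) = exp(−0.693) = 0.500. This reproduces the stated one half. The back-calculation that undoes it is C_trough = C_predose × exp(+ke × t); a pre-dose value of 50 gives 50 × 2.00 = 100.

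**2. The printed equation.** As printed, C_trough = C_predose + exp(−ke × t). With the same inputs this gives 50 + 0.50 = 50.5, not 100. The added term can never exceed 1 concentration unit. The rest of the check uses the multiplicative form.

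**3. Error from the fixed 7am.** Let s be the sampling time and u the participant's usual dosing time.

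- Plan: C_predose × exp(ke × (s − 7))
- Target: C_predose × exp(ke × (s − u))
- Ratio, plan to target: exp(ke × (u − 7))

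The sampling time s cancels. Only the distance of the usual time from 7am matters.

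**4. Size**, using the same half-life in both lines:

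| Half-life | ke per h | u 1 h later | u 1 h earlier | u 2 h later | u 2 h earlier |
|---|---|---|---|---|---|
| 2 h | 0.3465 | +41.4% | −29.3% | +100.0% | −50.0% |
| 2.5 h (plan) | 0.2772 | +31.9% | −24.2% | +74.1% | −42.6% |
| 3 h | 0.2310 | +26.0% | −20.6% | +58.7% | −37.0% |

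**5. Worked case.** Usual dose 9am, sample 10am, half-life 2.5 h. The right factor is exp(0.2772 × 1) = 1.32; the 7am rule gives exp(0.2772 × 3) = 2.30; and 2.30/1.32 = 1.74, an overstatement of 74%. The uncorrected sample is at exp(−0.2772) = 0.76 of the trough, 24% too low. For this participant the corrected value is further from the truth than the observed one. On the log scale that happens whenever the usual time is nearer to the sampling time than to 7am. For a 10am sample this means any usual time from after (7 + 10)/2 = 8:30am up to the sample.

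**6. The same error under the printed equation.** For t of 1 to 4 h, a 1 h error in t moves the result by only 0.08 to 0.24 concentration units, and in the opposite direction (a longer t gives a smaller value). At t = 3 h, for assumed pre-dose values of 1, 10 and 100 ng/mL, an hour too short or too long changes the result by +9.7%/−7.3%, +1.3%/−1.0% and +0.14%/−0.10%.

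**The case against.** Several points on the other side have force.

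- **The printed formula.** A reader might take 32% per hour as what the plan will produce. It is not: as step 6 shows, the additive equation barely responds to t. The percentages hold for the decay that the worked example describes. The equation is the larger defect in this section, but correcting it does not cure the 7am problem; it gives that problem its full effect.
- **7am is openly declared.** Table 1 states the assumption, and 12.5.2 makes planned time relative to dosing the default for derived parameters. But 9.1.1.1 defines the target as the trough before the usual dosing time, and a 7am value is that only for participants who do dose at 7am.
- **Availability of the data.** It is tempting to say the plan discards times it already holds. The SAP shows only that they are written in the diary. The items it names for transcription to the eCRF (Table 6 note 4 and 12.6.4) are stool counts, stool frequency scores and rectal bleeding scores. Whether dose times reach the database is not stated.
- **Consequences for inference.** A reader might infer a diluted exposure-response slope. Section 9.3 plans graphical exploration only and 9.1.1.1 rules out statistical analysis of the concentrations, so there is no planned regression to be attenuated.
- **Residual error.** Individual dosing times leave the fixed half-life in place. At t = 3 h the factor is 2.30 at 2.5 h, against 2.83 at 2 h and 2.00 at 3 h.

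**Conclusion.** The point stands as an improvement that should be made to an exploratory derivation. It does not threaten the primary safety objective or any planned test. A single 7am reference overstates the predicted trough by 32% per hour for later dosers and understates it by 24% per hour for earlier dosers, with ranges of +26% to +41% and −21% to −29% over the stated half-life. This assumes first-order decay in the multiplicative form and some spread of usual times around 7am; the SAP does not say how large that spread is.

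Two wider readings are not supported. The clinic's appointment time is not a source of this error, because it cancels (step 3), so appointment schedules cannot create differences between sites by this route. Nor are all PK/PD displays affected. Figures 4.8 to 4.17 also have biopsy pages, for which no back-calculation is defined. Figures 4.7 and 4.18 are titled with pre-dose concentrations, and observed values are still shown in Table 4.1, Figures 4.4 to 4.6 and Listing 45.

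**What to change.** Amend 9.1.1.1 and the matching row of Table 1 together:

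1. Correct the equation to C_trough = C_predose × exp(ke × t), so that it reproduces the worked example. Without this, individual times would change almost nothing.
2. Define t as the actual Day 43 sample time minus the participant's own usual morning dosing time, taken as the median of the diary-recorded morning dose times over a stated number of days before the visit.
3. Use 7am only where no diary time is available, and flag those values in Listing 45.
4. Show the 7am version as a sensitivity display beside the predicted-trough summary and the plasma pages of Figures 4.8 to 4.17.
5. State which concentration the biopsy pages of those figures plot.

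The cost is SAP wording and a short derivation. If dose times were not entered in the eCRF, a few days of diary times must be transcribed for about 24 participants, since only the active arm has received drug before the Day 43 pre-dose sample. No dosing or visit rule changes.

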9.1.2. Population of Interest

The PK analyses will be based on the Pharmacokinetic population, unless otherwise specified.

